7. ADDITIONAL INFORMATION ON STUDY PROCEDURES

7.1.1 Screening/Baseline

Subjects will be consented to the trial, and the CIPN Neuropathy 0-10 (and physical location) questionnaire will be administered. Subjects who score <2 on the CIPN Neuropathy 0-10 questionnaire will be a screen failure and will not be randomized or enrolled into the study. If CIPN Neuropathy 0-10 is answered sufficiently for inclusion (score ≥ 2), the rest of the baseline assessments are to be completed within two weeks from consent. Once eligibility is confirmed, subject will be randomized via CTMS to either Acupuncture (intervention arm) or Standard of Care. Subjects will be notified of their randomization result. Those randomized to Intervention Arm will begin acupuncture sessions within two weeks of enrollment.

7.1.2 Midpoint and Endpoint visits

The following assessments and questionnaires will be repeated at the Midpoint visit (Week 5 ± 1 week) and at the Endpoint visit (Week 10 ± 1 week) from randomization for the control arm. The assessments and questionnaires will be completed for the acupuncture arm at Midpoint visit (Week 5 ± 1 week) and Endpoint (Week 10 ± 1 week) from first acupuncture session. The questionnaires (see section 5.4) will be administered either in the clinic or via electronic survey or certified mail. The questionnaires should be completed with subjects in both arms, and regardless of whether the intervention (acupuncture) was received. Subjects in both arms will complete the study questionnaires at protocol defined timepoints, even if bortezomib/bortezomib-combination therapy is removed from their treatment regimen during the study (for those on active bortezomib treatment).

Note: These same assessments and questionnaires will be performed if the subject has an Early Termination visit (see study calendar).

See section 5.4 for more detailed information on the study questionnaires.

- Collect AESI information, if applicable (for those on acupuncture arm)
- Collect chemotherapy regimen information.
- CIPN: Neuropathy 0-10
- CIPN: Neuropathy physical location
- CIPN: FACT-GOG-NTX
- Other symptoms (constipation, dizziness, dry mouth)
- CDC HRQOL-4
- Morphine Equivalent Daily Dose (Past 7-day recall)
- Concomitant medication intake (Past 7-day recall)

7.1.3 Collection of AESIs

Subjects on the Intervention arm will be asked specifically at the Midpoint and Endpoint timepoints if they have had any of the designated AESIs. If subject happens to report an AESI or

if there is documentation in the EMR of an AESI at any other time during the study, starting at first acupuncture session, the study team will collect this information. See Section 10.1 for further details including timeframe for collection of AESIs.

7.1.4 Acupuncture

The acupuncture procedure and specific acupoints will be performed in accordance with the Revised Standards for Reporting Interventions in Clinical Trials of Acupuncture (STRICTA) guidelines⁶⁷ in **Appendix A**. Acupuncture in this study will occur twice during weeks 1-2, then once weekly during weeks 3-10. During Week 1 and Week 2, if an acupuncture session is missed, it may be made up the following week (there will be 3 sessions that following week). During Weeks 3-10, no sessions will be made up if missed. The date of acupuncture sessions completed and acupoints received will be documented. Subjects may continue to receive acupuncture sessions per protocol even if bortezomib or bortezomib-combination treatment is discontinued. Subjects should continue per protocol acupuncture sessions even if their neuropathy resolves.

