5.1 Study Intervention

Study subjects in the intervention arm will experience acupuncture in a group setting when possible to resemble the conditions of regular clinical practice at Levine Cancer Institute, therefore enhancing external validity and the ability to apply the conclusions of the study to “real-world” contexts outside of the study setting. For as long as COVID-19 is a concern, the acupuncture team will follow these additional safety measures: subjects will be seated at an appropriate distance apart and wear masks, and additional time will be allotted between sessions to allow for additional, thorough cleaning/sanitizing of equipment.

The acupuncture sessions will begin with a more intensive, twice weekly treatment for the first two weeks and taper to once per week for the remaining eight weeks. This amounts to 12 total sessions over approximately 10 weeks.

The acupuncture procedure and specific acupoints will be performed in accordance with the Revised Standards for Reporting Interventions in Clinical Trials of Acupuncture (STRICTA) guidelines⁶⁷ in **Appendix A**.

Consenting and all conversations with subjects regarding their medical history and medications will be held privately. Questionnaires will also be administered privately. All subjects will be able to answer the questionnaires via two options: 1) on paper (in person or via certified mail) or 2) via RedCap electronic survey. Phone contact for questionnaires is acceptable if unable to be completed by other stated routes. The form of questionnaire administration will be based on the appointment situation, needs and/ or preference of the subject, and subject access to technology (e.g., computer, tablet, smartphone). Subject will need to be willing to provide an active email to which the questionnaires can be sent to utilize the electronic survey option.

Subjects randomized to the control arm will have their CIPN treated by their physician per standard of care. Subjects randomized to the intervention arm will begin acupuncture sessions within two weeks of enrollment and will continue their SOC treatment for CIPN as per their physician.

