6. STUDY CALENDAR

Procedures/Assessments	Screening Visit	Baseline (complete within 2 weeks from consent, can be done at screening AFTER Randomization)	Weeks 1-2 ² : Twice per week	Weeks 3-10 ² : Once per week	Week 5 ± 1 week ^{3,5} Midpoint	Week 10 ± 1 week ^{3,5} Endpoint	Early Termination (if applicable) ⁷	Follow Up (30 days [+7] from last Acup tx)
Informed Consent Form	X							
Randomization via CTMS (within 2 weeks from consent)		X ¹²						
Sociodemographics & Medical History (see 5.3.1 and 5.3.2)		X						
Multiple Myeloma status ⁶		X						
ECOG	X							
Height / Weight/ BMI		X						
Acupuncture Expectancy Scale ⁴		X ⁴						
Acupuncture Treatment ^{1,2}			X ²	X ²				
Collect Chemotherapy regimen information ¹⁰	X					X	X	
Adverse Events of Special Interest ⁸			Continuously, starting at First Acupuncture session			X	X ¹³	
CIPN: Neuropathy 0-10 & neuropathy physical location	X ¹¹				X	X	X	
CIPN: FACT-GOG-NTX		X ¹⁴			X	X	X	
Other Symptoms: Constipation, dizziness, dry mouth		X ¹⁴			X	X	X	
Quality of Life: CDC HRQOL-4		X ¹⁴			X	X	X	
Opioid Intake/ Morphine Equivalent Daily Dose (see Appendix B)		X ⁹			X	X	X	
Concomitant Medication: (See Section 5.3.4 for which medications to collect)		X ⁹			X	X	X	

Key to Footnotes

¹ First acupuncture session to occur within 2 weeks of enrollment (date randomized). Acupuncture treatment schedule to start on a Monday or Thursday only.

² Week 1 for subjects on the acupuncture/intervention arm is the week when the first acupuncture session occurs. Window for acupuncture sessions during Week 1 and Week 2 is at least 1 day (minimum) and no more than 8 days (maximum) between visits. Window for sessions during Weeks 3-10 is at least 2 days (minimum) and no more than 9 days (maximum) between visits. During Week 1 and Week 2, if an acupuncture session is missed, it may be made up the following week (there will be 3 sessions that following week). During Weeks 3-10, no sessions will be made up if missed.

³ Questionnaires at Midpoint and Endpoint should still be collected even if subject decides to discontinue the acupuncture sessions but is willing to stay on study. Week 1 for the control group begins at Randomization.

⁴ Acupuncture Expectancy Scale questionnaire to be collected only from subjects on Intervention (Acupuncture) arm at any time AFTER Randomization has occurred, but PRIOR to first acupuncture session.

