11.3.4 Definition of Exploratory Endpoints

- Opioid use
 - Opioid use assessed through Morphine Equivalent Daily Dose (MEDD) will be calculated for each subject as a quantitative value.
- Concomitant medication use
 - Concomitant medication use assessed through medication name and dose will be determined for each subject.
- Acupuncture administration
 - Acupuncture administration will be defined for each subject on the acupuncture arm as the number of attended acupuncture sessions from 0 to 12.
- Acupuncture expectancy
 - The acupuncture expectancy score will be captured quantitatively for each subject as a composite score ranging from 4 to 20.

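### The make-up rule states three sessions in the following week for a miss in Week 1 or Week 2; after a single Week 2 miss this totals 13 sessions, not 12

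*Combined protocol and SAP*

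**What the plan says.** Section 7.1.4 sets the frequency: "Acupuncture in this study will occur twice during weeks 1-2, then once weekly during weeks 3-10". Section 5.1, the study calendar and Appendix A (items 3a and 3b) make clear that the first part means two sessions in each of Weeks 1 and 2. Section 5.1 adds up the course: "This amounts to 12 total sessions over approximately 10 weeks". Appendix A gives the same total.

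For a session missed in Week 1 or Week 2, Section 7.1.4 says "it may be made up the following week (there will be 3 sessions that following week". Footnote 2 of the calendar (Section 6) repeats the rule. Both places cover the two weeks in one sentence with one figure. For the later weeks: "During Weeks 3-10, no sessions will be made up if missed".

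On the analysis side, Section 11.3.4 defines acupuncture administration "as the number of attended acupuncture sessions from 0 to 12". Section 11.5.7 groups that count into five levels: 0, 1–3, 4–7, 8–11 and 12 sessions.

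Footnote 2 also sets spacing limits. For the later weeks: "Window for sessions during Weeks 3-10 is at least 2 days (minimum) and no more than 9 days (maximum) between visits".

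**The concern.** The week after Week 1 and the week after Week 2 do not carry the same number of scheduled sessions: Week 2 has two and Week 3 has one. A single stated figure for the following week therefore cannot describe the replacement of one session in both cases and still lead to one course total.

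Two things are at stake. First, a subject who misses one Week 2 session could be given a different number of sessions depending on which sentence staff follow, and Section 13.3 requires conduct exactly as described. Second, a count of 13 has no place in the exploratory dose variable: it lies outside the stated range and belongs to none of the five levels, so the analyst would have to settle its handling after the fact.

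**Working it through.** **Inputs.** Two sessions in each of Weeks 1 and 2, and one in each of Weeks 3 to 10 (Sections 5.1, 6 and 7.1.4; Appendix A). Stated total 12 (Section 5.1; Appendix A). Three sessions in the week after a missed Week 1 or Week 2 session (Section 7.1.4; calendar footnote 2). Dose variable 0 to 12, top level exactly 12 (Sections 11.3.4 and 11.5.7).

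**Step 1: the plan's own total.** Total = Week 1 + Week 2 + Weeks 3 to 10 = 2 + 2 + 8 × 1 = 12. The stated figure reproduces.

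**Step 2: apply the make-up rule.** The sum is Week 1 + Week 2 + Week 3 + Weeks 4 to 10. The literal column sets the following week to three sessions. The other column adds one session for each one missed. It is shown only to locate the discrepancy, not as a recommendation.

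| Sessions missed | Literal (three in the following week) | One added per session missed |
|---|---|---|
| One in Week 1 | 1 + 3 + 1 + 7 = 12 | 1 + 3 + 1 + 7 = 12 |
| One in Week 2 | 2 + 1 + 3 + 7 = **13** | 2 + 1 + 2 + 7 = 12 |
| Both in Week 2 | 2 + 0 + 3 + 7 = 12 | 2 + 0 + 3 + 7 = 12 |

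The figure of three agrees with the 12-session course after one Week 1 miss or after two Week 2 misses. It disagrees after one Week 2 miss, by 13 − 12 = 1 session, or 1/12 ≈ 8% of the course.

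**Step 3: compare with the dose variable.** A count of 13 exceeds the maximum of 12 and fits none of the levels 0, 1–3, 4–7, 8–11 or 12.

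**Step 4: the spacing limit in Weeks 3 to 10.** If the Week k session is missed and not replaced, the gap between attended visits is 14 + b − a days, where a and b are the weekday positions of the visits in weeks k − 1 and k + 1. On the same weekday the gap is 14 days. Over all combinations:

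| Session days allowed | Gap (days) | Pairs at 9 days or less |
|---|---|---|
| Any day | 8 to 20 | 3 of 49 |
| Monday to Friday | 10 to 18 | 0 of 25 |
| Monday or Thursday only | 11 to 17 | 0 of 4 |

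If only the days in between are counted, 1 of the 25 Monday-to-Friday pairs meets the limit. A missed Week 10 session has no later visit and so creates no gap.

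**The case against.** The strongest reply is that the operative clause is singular and permissive: one missed session may be replaced, and a third Week 3 session would replace nothing. The parenthesis then reads as an aside written with Week 1 in mind. The 12-session total recurs across the document, and the compliance rule in Section 11.4 counts sessions out of 12. On this view the documents taken together do not call for a 13th session. Much of this stands: the make-up is optional, and replacing one session with one is a natural reading. It does not remove the error. The figure of three is stated flatly, appears in two places, and belongs to a sentence that names Week 2. It also fits two missed Week 2 sessions, but the sentence speaks of one.

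It is also fair to say that little depends on it. A subject with 13 sessions would still meet the compliance threshold of at least nine. The primary endpoint (Section 11.3.1) uses only the baseline and Week 10 neuropathy scores.

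A reader might go further and infer from footnote 2 that the nine-day maximum cannot be met whenever a weekly session is missed, so that every such miss is automatically a window deviation. The documents do not support that. A missed Week 10 session has no following visit, and a few pairs of days fall within nine days. The calendar restricts only the day on which the schedule starts: "Acupuncture treatment schedule to start on a Monday or Thursday only". Footnote 2 does not say that the limit runs across a missed, unreplaced session, and nothing in the documents classes the resulting gap as a separate deviation. No analysis uses the interval. What remains is a missing detail: a miss in Weeks 3 to 9 will normally leave more than nine days between attended visits, and the text does not say whether the window then applies.

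**Conclusion.** The make-up rule is wrong as written for one case, a single missed Week 2 session. Read literally it gives 13 sessions, against a stated 12 and a dose variable that ends at 12. This rests on taking the parenthesis at face value and on Week 3 having one scheduled session, which the documents state consistently.

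The point is minor. It reaches only delivered sessions and the exploratory dose-response analysis. The primary endpoint, its Fisher test, the power and the intervention-compliant population do not change. The number of subjects affected cannot be worked out, because the documents give no attendance figures. It would depend on how many miss exactly one Week 2 session, how many take up the optional replacement, and whether staff then follow the parenthesis.

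The spacing limit is not a contradiction. It deserves at most a clarifying sentence.

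**What to change.** Reconcile Sections 5.1, 6 (footnote 2), 7.1.4, 11.3.4 and 11.5.7 with Appendix A:

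- In footnote 2 and Section 7.1.4, state the number of sessions in the following week separately for a Week 1 miss and a Week 2 miss, so that the course has a single total.
- Make the range in Section 11.3.4 and the top level in Section 11.5.7 agree with that total.
- Optionally, say in footnote 2 whether the spacing window applies across a missed session that is not replaced.

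Which figure and rule stand is for the clinical team to decide. The cost is a few words in two places that describe the schedule and, if needed, a line in the analysis sections. No extra data are required and the sample size does not change.

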8. REMOVAL OF SUBJECTS FROM STUDY

8.1 Off Treatment

If subjects on the acupuncture arm decide to discontinue the acupuncture sessions but continue the questionnaires and other assessments, they will be considered Off Treatment. Reasons for coming off treatment would include, but not be limited to:

- Completed protocol therapy
- Adverse event (toxicity)
- Non-compliance
- Investigator decision
- Consent withdrawal for acupuncture sessions
- Subject death
- Study closure

8.2 Off Study

Once all on-study assessments and procedures are completed, subject will be considered Off Study. Subjects on the acupuncture arm will be followed for AESIs for 30 days post the last acupuncture session, then they will be Off Study.

Subjects may stop their participation in this study at any time if they no longer wish to participate, or if the investigator believes this to be in the best interest of the subject.

When subjects are removed from the study, the reason for study removal and date the subject was removed should be documented. Reasons a subject may be removed from study include, but are not limited to:

- Subject non-compliance with study participation, in the opinion of the investigator
- The subject withdraws study consent
- The subject is lost to follow-up
- Investigator's decision to withdraw the subject

- Subject death

Subjects that are Off Study will not participate in any study related procedures, including data collection.

9. DATA AND SAFETY MONITORING PLANS

9.1 Safety Monitoring

This protocol will be monitored according to the processes in effect for all LCI investigator-initiated studies and the protocol-specific monitoring plan and will abide by standard operating procedures (SOPs) set forth by both Atrium Health Office of Clinical and Translational Research and the LCI Clinical Trials Office. It is the responsibility of the Sponsor-Investigator to monitor any safety data (i.e., unanticipated problems/potential risks as per Section 9) for this study. The Sponsor-Investigator, Statistician, and other team members as needed will meet regularly to monitor subject consents, enrollment and retention, safety data, and validity/integrity of the data. Documentation of these meetings will be kept with the study records. The Sponsor-Investigator will submit data to the LCI Data and Safety Monitoring Committee as required.

9.2 Data Monitoring

This study will be organized, performed, and reported in compliance with the study protocol, SOPs of the LCI and Atrium Health Office of Clinical and Translational Research (and/or other participating institutional SOPs), and other applicable regulations and guidelines (e.g. GCP).

Subjects will be monitored by LCI Quality Assurance Monitors per the study-specific monitoring plan and LCI/Atrium Health SOPs for data quality. Data from this study will be collected on electronic case report forms (eCRFs) and stored in the study database. Monitoring will be done by comparing source documentation to the eCRFs. Any variation between the two data sets will be discussed with the investigator, Sponsor-Investigator and/or other study team members as appropriate.

The study database will be reviewed and checked for omissions, apparent errors, and values requiring further clarification using computerized and manual procedures. Data queries requiring clarification will be generated and addressed by the appropriate study team member. Only authorized personnel will make corrections to the study database and all corrections will be documented in an electronic audit trail.

It is important for the investigators and their relevant personnel to be available during the monitoring visits and for sufficient time to be devoted to the process.

10. POTENTIAL RISKS/UNANTICIPATED PROBLEMS

10.1 Adverse Events of Special Interest

Adverse Events of Special Interest will be collected only for those subjects on the intervention arm, beginning with start of first acupuncture session. AESIs will be collected through 30 days post last acupuncture session. Subjects who experience an AESI will be medically managed by their physician or acupuncturist through standard of care, as appropriate. These events should only be captured if deemed **related** to the acupuncture intervention per the Investigator.

All AESIs will be graded per CTCAE 5.0.

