1.1.3 Current Treatments for CIPN

There are no cures for CIPN; it can only be treated.¹⁷ Treatments for CIPN include concomitant medications which target various pathophysiological mechanisms. Pharmacologic options include anticonvulsants (e.g., gabapentin, (Neurontin®, Gralise®), antidepressants (e.g., duloxetine (Cymbalta®)), over-the-counter (e.g. aspirin, ibuprofen), prescription (e.g., celecoxib (Celebrex®)), non-steroidal anti-inflammatory drugs (NSAIDs), and opioids in severe cases unresponsive to other treatments. Topical agents (e.g., amitriptyline, lidocaine) applied to the skin are also options.^{18,19} These treatments, however, are not universally effective. Menthol and capsaicin can be used but¹⁸ have side effects and there is limited evidence to support their clinical use.⁶ Side effects of anticonvulsants include drowsiness and dizziness, and antidepressants are associated with dry mouth, nausea, drowsiness, dizziness, decreased appetite and constipation.²⁰ Nonpharmacologic options with varying levels of efficacy include neurostimulation, exercise, nonpharmacologic menthol and capsaicin topical agents, and

acupuncture.¹⁸ For patients open to integrative modalities to lessen CIPN symptoms, acupuncture is a promising intervention.

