4. SUBJECT ALLOCATION

4.1 Randomization

Subjects will be randomized in a 2:1 fashion to either acupuncture plus standard subject management or standard of care alone and assigned a Sequence Number. This will be accomplished utilizing the CTMS, whereby a list of Sequence Numbers and associated treatment arm assignments randomly generated prior to study activation will be uploaded by a member of the Levine Cancer Institute Biostatistics Core. The Sequence Number will be a four digit, randomly generated ID number, ranging from 0001 to 9999. A stratified block randomization will be utilized including the following stratification factors to reduce confounding of comparisons between the treatment arms:

- Baseline neuropathy score (neuropathy score 2 – 6 vs 7 – 10)

Blinding will not be possible within this trial because the subjects and study personnel will be able to decipher intervention from control based on the study activities. Those exposed to acupuncture will understand that they are in the intervention group and those given standard of care only will understand that they are in the control group. If a subject in the control group has an acupuncture session while enrolled, they will be discontinued from the study and all further assessments at that point.

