10.1.2 Other AESI

Other potential adverse events to be documented and followed in this study are noted below. However, these should only be captured if they are deemed **related** to the acupuncture intervention per the Investigator.

- Dizziness, Grade ≥ 2
- Syncope, Grade ≥ 3
- Fatigue, Grade ≥ 2
- Hyperhidrosis, (Sweating) Grade ≥ 2

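### Listed AESIs enter the safety data only if the unblinded Investigator judges them related to acupuncture, but the endpoint and analysis sections report them without that qualification, and the AESI dataset cannot show how far the rates depend on attribution

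*Combined protocol and SAP*

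**What the plan says.** All references are to the combined protocol and SAP.

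- **Capture (10.1, 10.1.2).** For all AESIs: "These events should only be captured if deemed related to the acupuncture intervention per the Investigator". The rule is restated for the four systemic terms, dizziness, syncope, fatigue and hyperhidrosis: "However, these should only be captured if they are deemed related to the acupuncture intervention per the Investigator". Each listed term already has a minimum CTCAE grade.
- **Arm and window (10.1).** "Adverse Events of Special Interest will be collected only for those subjects on the intervention arm, beginning with start of first acupuncture session". Collection runs to 30 days after the last session.
- **Ascertainment (7.1.3).** "Subjects on the Intervention arm will be asked specifically at the Midpoint and Endpoint timepoints if they have had any of the designated AESIs". AESIs that come up at other times, by subject report or in the EMR, are also collected. The section refers to 10.1 for details, so the relatedness limit applies there too.
- **Blinding (4.1).** "Blinding will not be possible within this trial because the subjects and study personnel will be able to decipher intervention from control".
- **Endpoint and analysis (11.3.3, 11.5.6).** The endpoint is a yes/no variable per subject for having had an AESI, by preferred term, system organ class and overall. It is summarized in the acupuncture arm with Clopper-Pearson 95% intervals. Neither section mentions attribution.
- **Oversight (9.1).** "It is the responsibility of the Sponsor-Investigator to monitor any safety data". Regular team meetings include the statistician, and data go to the DSMC as required.

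**The concern.** Relatedness is usually an attribute recorded for an event. Here it is a condition for recording the event, applied after the lists have already been narrowed by term and grade. Someone reading only 11.3.3 and 11.5.6 would take the proportions as occurrence of the listed events, when they are occurrence as attributed by one unblinded person.

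This matters most where attribution is hardest. Section 1.1.7 names fatigue, sweating and faintness among acupuncture's adverse effects and says that cancer patients are at higher risk of adverse events. Section 1.1.3 supplies a competing cause for some of the same complaints: "Side effects of anticonvulsants include drowsiness and dizziness, and antidepressants are associated with dry mouth, nausea, drowsiness, dizziness". Under 5.1, acupuncture subjects continue their usual CIPN treatment. A run of Grade 2 dizziness events, each reasonably put down to medication, would not appear in the AESI dataset. Nobody working from that dataset could ask whether the run as a whole looked like chance.

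**Working it through.** The plan states no expected AESI rate, no share expected to be related and no target precision for safety, so there is no planned figure to reproduce. The check is a comparison of sections followed by an illustration.

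**Step 1: is attribution defined or reviewed?** The protocol gives no causality scale, no rule for possibly related events, no log of events judged unrelated and no second review. By contrast, the definition of an unanticipated problem in 10.4.1 expressly admits events that are possibly related.

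**Step 2: does another planned source fill the gap?**

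- *Medical record.* It may document the event. No step brings an event judged unrelated into the AESI data.
- *Source-to-eCRF monitoring (9.2).* It compares source with what is entered. An event judged unrelated need not be entered, and no check of the attribution is described.
- *Questionnaires (5.4.4, 5.4.5, 11.3.2).* Dizziness and lack of energy are scored in both arms at baseline, midpoint, endpoint and early termination. The scores use 7-day recall and carry no CTCAE grade, event date or attribution. They do not reach into the 30-day follow-up, and no item described covers syncope or sweating.
- *Unanticipated problems (10.4.1).* These must be unexpected, so events already listed as anticipated would ordinarily not qualify.

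These sources narrow the gap for dizziness and fatigue. None rebuilds the AESI rates.

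**Step 3: how far can the reported figure move?**

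Inputs:
- Enrolment of 75 (11.2) at 2:1 (4.1): n = 75 × 2/3 = 50 acupuncture subjects.
- Assumed: 10 of the 50 have a listed event of a given term at its stated grade.
- Assumed: a share s of those 10 is judged related, from 0 to 1.

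Formulas: recorded count k = 10 × s; reported proportion = k/n. The Clopper-Pearson limits are the 2.5% quantile of Beta(k, n − k + 1) and the 97.5% quantile of Beta(k + 1, n − k), with a lower limit of 0 when k = 0.

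| Share judged related (s) | k | Reported | 95% interval |
|---|---|---|---|
| 0 | 0 | 0% | 0 to 7.1% |
| 0.2 | 2 | 4% | 0.5 to 13.7% |
| 0.5 | 5 | 10% | 3.3 to 21.8% |
| 0.8 | 8 | 16% | 7.2 to 29.1% |
| 1 | 10 | 20% | 10.0 to 33.7% |

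With 5 subjects affected instead of 10 the reported figure can run from 0% to 10%; with 15, from 0% to 30%. The interval carries sampling error only. Given a recorded k of 2, the dataset cannot say whether 2, 5 or 15 subjects had the listed event. If all listed events were recorded with attribution as a field, both counts would be visible.

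**The case against.** The strongest reply is that this is a deliberate choice. The rule is stated twice, and the safety objective (2.1.3) is only to summarize AESIs in acupuncture subjects. On that view the target is acupuncture-attributed events, 11.3.3 and 11.5.6 estimate exactly that, and competing drug causes are a reason to want an attribution filter. This stands in large part: the plan does not contradict itself, and only misattribution would be bias. What remains is that the endpoint and analysis sections do not state the restriction, and that the recorded data cannot show whether attribution was sound.

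Two stronger readings are tempting, and the documents do not support either.

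- *A reader might infer that events judged unrelated leave no trace and can never be verified.* The text says only that they are not captured as AESIs. The EMR may hold them, monitors see source records, and dizziness and lack of energy are compared between randomized arms by questionnaire. Sections 9.1 and 9.2 also defer to monitoring plans and SOPs outside these documents, where attribution decisions might be logged.
- *A reader might infer from the table that a reported 4% understates a true 20%.* The 20% is an assumed all-cause rate, which is not the benchmark for a related-event endpoint. Nothing in the documents estimates misattribution.

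It is also fair to say that the remedy is partial. Without control-arm collection, an all-cause rate of fatigue or dizziness in these patients mixes acupuncture effects with background, and the related column still rests on the same unblinded judgement.

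**Conclusion.** The point holds as a worthwhile, inexpensive improvement; it does not identify an error. The unblinded Investigator's judgement determines which listed events enter the AESI dataset, and the reporting sections do not say so. As a result, neither the attribution nor a pattern across subjects can be reviewed from that dataset. The rule also covers needle-site events, where attribution is easier; dizziness, fatigue, syncope and sweating are the terms most exposed.

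The size cannot be stated from the documents. By construction, the reported proportion lies between zero and the all-cause proportion of listed events. The numerical range rests wholly on assumed rates with about 50 acupuncture subjects. The safety analysis is descriptive, the termination criteria in 12.2 set no numerical safety threshold, and the primary efficacy analysis is unaffected. The conclusion assumes that no log of rejected events is required by a monitoring plan or CRF that is not shown.

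**What to change.** - **10.1 and 10.1.2:** replace the related-only capture rule. Record every listed event at its stated grade in acupuncture-arm subjects, within the existing window, with Investigator relatedness as a CRF field. Terms, grades, arm and window stay as they are.
- **11.3.3 and 11.5.6:** report each term twice, all-cause and Investigator-related, and label the columns accordingly. The related-only table now planned is kept.

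Subjects are already asked about the designated AESIs at midpoint and endpoint, and the Investigator must already judge relatedness, so the main change is to retain a decision that is being made anyway. The change should be made before collection ends, because events not entered may be hard to recover.

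Cost: wording in four sections, one CRF field, and more events to grade and enter, possibly many for fatigue and dizziness. The all-cause column will include background symptoms and has no control-arm comparator. It should be presented as showing how far the related-only rate depends on attribution, and not as an estimate of acupuncture risk. If the sponsor keeps the present capture rule, the minimum is to label the endpoint as Investigator-attributed AESIs, which corrects the description but leaves attribution unauditable from the dataset.
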